3.5 Anesthesia

Patients will receive general anesthesia.

3.7 Primary endpoint

Disease Free Survival. Occurrence of Disease Free Survival. If such an episode occurs, then it will be defined as=1 'YES' If such an episode does not occur, then it will be defined as=0 'NO'. [Time Frame: 3 years postoperatively]

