3.3 Inclusion / Exclusion Criteria

Inclusion criteria are the following [10]:

- Histologically confirmed rectal adenocarcinoma
- cT3, cT4, threatened CRM / MRF, EMVI (+), $\geq N1$
- Multidisciplinary tumor board decision for neoadjuvant treatment
- Tumor distance from the anal verge ≤ 15 cm based on endoscopy or magnetic resonance imaging
- Patient 18 to 80 years old
- General health condition status WHO 0-1
- Absence of co-morbidities that may affect treatment
- Neutrophils $> 1,500$ / mm³, platelets $> 100,000$ / mm³, hemoglobin > 10 g / dL, normal creatinine, and creatinine clearance > 50 mL / min
- Signed informed consent of the patient

Exclusion criteria are the following:

- Distant metastases
- Non-resectable cancer
- Contraindications for the administration of chemotherapy
- Previous pelvic radiotherapy or chemotherapy

- History of inflammatory bowel disorders
- History of angina, acute myocardial infarction or heart failure
- Active sepsis or systemic infection
- Untreated physical and mental disability
- Synchronous malignancy
- Pregnancy or breast-feeding
- Lack of compliance with the protocol process
- Non-granting of signed informed consent

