3.4 Study Arms

In this study there will be two arms [5, 10]. Patients that are randomized in the first arm will receive neoadjuvant chemoradiotherapy and consolidation chemotherapy and then undergo surgical resection of the tumor. In the second arm, patients will receive the standard long-course neoadjuvant chemoradiotherapy regimen and then undergo tumor resection. The treatment will be completed with adjuvant chemotherapy. In both groups, surgery will follow the principles of total mesorectal excision (TME).

The control group will receive the standard 5-week neoadjuvant chemoradiotherapy regimen. Six weeks after completion the patient will be re-staged with rectal MRI and depending on the response will be operated (TME): immediately in case of non-response (mrTRG 5) or after an additional 6-week delay (overall 12 weeks after the end of chemoradiotherapy) in case of partial response (mrTRG 2-4). Adjuvant chemotherapy will be, also, administered.

The experimental group will receive the standard 5-week neoadjuvant chemoradiotherapy (CRT). Thereafter, all patients will commence consolidation chemotherapy. At the 6th week after the end of CRT, patients will undergo MRI re-staging: In case of non-response (mrTRG 5) they will be submitted immediately to surgery, and, subsequently, excluded from the trial. In case of response (mrTRG 2-4) they will receive consolidation chemotherapy for the whole waiting period between the end of CRT and surgery - 12 weeks.

The following interventions will be introduced:

Neoadjuvant Chemoradiotherapy. 5-week neoadjuvant radiotherapy regimen (28 x 1.8 Gy) combined with Capecitabine (bid 800 mg/m², twice daily, on days 1-33-38)

Consolidation Chemotherapy. CAPOX (Capecitabine bid 1000 mg/m² and Oxaliplatin 130 mg/m², day 1, every 3 weeks) or alternatively FOLFOX

Adjuvant Chemotherapy. 8 cycles of CAPOX (Capecitabine bid 1000 mg/m², twice daily, day 1-14, every 3 weeks and Oxaliplatin 130 mg/m², day 1, every 3 weeks) or alternatively, 12 cycles of folinate, fluorouracil and oxaliplatin (FOLFOX)

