3.10 Randomization

The randomization of the patients will be performed using a dedicated software with a 1:1 allocation ratio. The allocation group will be concealed with opaque envelopes.

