3.13 Monitoring

Following hospital discharge, the patient will be called for reassessment at one month after the operation. Patients will be included in the standard monitoring protocol (CT, MRI, cancer markers), unless otherwise required. At the same time, the pathological assessment of the specimen will be recorded. In addition, at 3 and 5 years postoperatively, overall, disease-free survival and recurrence rates will be recorded.

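### The only date given for DFS, OS and local recurrence is counted from surgery, so failures before surgery and patients never operated on have no defined place in the primary comparison

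*Protocol*

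**What the plan says.** Section 3.7 defines the primary endpoint, DFS, as a yes/no outcome with the bracket "Time Frame: 3 years postoperatively". In 3.8 the same bracket stands on overall survival (OS) and local recurrence, and also on chemotherapy toxicity and treatment compliance. Section 3.13 makes the date operational: "at 3 and 5 years postoperatively, overall, disease-free survival and recurrence rates will be recorded". The first visit it names is also postoperative: "Following hospital discharge, the patient will be called for reassessment at one month after the operation".

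Section 3.4 sets the order of events: "Patients that are randomized in the first arm will receive neoadjuvant chemoradiotherapy and consolidation chemotherapy and then undergo surgical resection of the tumor". Control patients are operated on "immediately in case of non-response (mrTRG 5) or after an additional 6-week delay (overall 12 weeks after the end of chemoradiotherapy"), the later date applying to mrTRG 2-4. The experimental arm has its re-staging MRI at the same week 6 and, for mrTRG 2-4, the same 12-week interval. Experimental patients with mrTRG 5 go a different way afterwards: "they will be submitted immediately to surgery, and, subsequently, excluded from the trial". Nothing similar is written for control patients with mrTRG 5, and no route is written for mrTRG 1 in either arm.

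The time of randomisation is implied rather than stated. Section 3.10 says "The randomization of the patients will be performed using a dedicated software with a 1:1 allocation ratio" and gives no date. Because 3.4 has randomised patients go on to chemoradiotherapy (CRT), and 3.3 excludes "Previous pelvic radiotherapy or chemotherapy", randomisation before CRT is the natural reading.

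**The concern.** A time origin in a randomised comparison should be the same event for everyone and should not be open to influence by treatment. Surgery is neither. It lies months after randomisation, and the tested chemotherapy is given in between. Section 1.1 itself says that neoadjuvant chemotherapy raises severe toxicity, so a difference between arms in who reaches surgery, and when, cannot be ruled out.

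Two groups are affected. Patients who progress or die before surgery may be counted as failures or left out, depending on how the bracket is read. Patients who are alive but not operated on have no 3-year date under either reading. In a trial of 84 patients with few expected events, a handful of such patients matters.

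**Working it through.** **Inputs.** From the protocol: 5 weeks of CRT; MRI at week 6 and surgery at week 6 or 12 after CRT (3.4); hazard ratio 0.23, alpha 5%, power 90%, dropout 15%, 42 per group (3.9). Not given, and therefore assumed: control 3-year DFS, sidedness of alpha, the number of preoperative failures, and the gap between randomisation and start of CRT (taken as zero).

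**Timing.** From the start of CRT, surgery falls at 5 + 6 = 11 weeks (mrTRG 5) or 5 + 12 = 17 weeks (mrTRG 2-4). Three years after surgery is then up to 156 + 17 = 173 weeks.

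**The plan's own figure.** Without a control DFS, 42 per group can be reached but not confirmed. For example, two proportions of 50% and 0.50^0.23 = 85.3%, two-sided, need 35 per group, and 35/0.85 = 41.2, rounded up to 42. Since 42 already includes dropout, 42 × 0.85 = 35.7, about 36 evaluable per arm.

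**Events needed.** With (z_alpha + z_beta)² = 10.51 two-sided or 8.56 one-sided:

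| Formula | Two-sided | One-sided |
|---|---|---|
| Schoenfeld, 4(z_alpha + z_beta)²/(ln 0.23)² | 19.5, so 20 | 15.9, so 16 |
| Freedman, (z_alpha + z_beta)² × (1.23/0.77)² | 26.8, so 27 | 21.9, so 22 |

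**Implied control DFS (S).** Solving 35.7 × [(1 − S) + (1 − S^0.23)] = 20 gives S of about 56% (experimental 88%). Setting it to 27 gives about 42% (experimental 82%).

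**Patients operated on as planned.** The 6 weeks between the two surgery dates move control 3-year DFS by S − S^(162/156). That is 1.3 points at S = 50% and 0.8 at S = 75%, and the schedule is the same in both arms.

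**One patient who is not.** Changing one code moves an arm's rate by 1/42 = 2.4 points. Leaving a failure out instead of coding it 0 raises that arm's rate by p/42, where p is the rate in the remaining patients. This is 2.0 to 2.1 points in the experimental arm (p = 82% to 90%) and 1.0 to 1.5 in the control arm (p = 42% to 63%). Omission flatters whichever arm loses the failure, so the direction is not fixed in advance.

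**Scale of preoperative failure.** If the hazard before surgery equalled that afterwards, 1 − S^(17/156) gives 7.3% to 3.1% of control patients for S = 50% to 75%, about 3 to 1 of 42. In the experimental arm it is 1.7% to 0.7%, fewer than one. This is an illustration only.

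**Effect of the fix on follow-up and power.** A landmark 3 years after randomisation leaves 156 − 17 = 139 weeks after surgery. With all 42 per arm followed (S = 63% or 50%), expected postoperative events fall from 20 to 18.2 or from 27 to 24.7, about 8% to 9%. Simulated power (two-sided 5% log-rank, exponential times after surgery at week 17, no preoperative failures) falls from 86% to 82% or from 95% to 93%.

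With 15% dropout at uniform times, the rates calibrated to about 36 evaluable per arm, and 0 to 4 counted preoperative failures in each arm, power at that landmark is:

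| Calibration | 0 failures | 4 failures |
|---|---|---|
| 20 events, control DFS about 56% | about 85% | about 68% |
| 27 events, control DFS about 42% | about 95% | about 87% |

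**The case against.** A reader might infer that the protocol restricts the primary analysis to operated patients, or that the timing favours the experimental arm. The documents support neither.

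- The same bracket stands on chemotherapy toxicity and treatment compliance, which must include preoperative treatment, so it may mark only the end of observation. Read that way, a preoperative death or progression is simply not disease-free and is coded 0.
- No section limits the analysis to operated patients.
- Surgery is scheduled at the same response-based times in both arms, and every pathway written in 3.4 ends in surgery.
- Watch-and-wait appears only in the literature review, as a theoretical benefit, not as a planned result of this trial. The toxicity statement there does not say that fewer patients reach surgery.
- Section 3.13 also puts patients on a standard monitoring protocol, and 3.4 schedules an MRI before surgery, so an unoperated patient is not necessarily unmonitored.
- A statistical analysis plan, not shown here, may settle the coding of such patients.

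These points limit the concern to preoperative failures and unoperated patients. They do not remove it. The protocol itself fixes the date, in three sections, and an endpoint date counted from surgery does not exist for someone who has none. The mrTRG 1 category, for which 3.4 writes no route, shows that the gap is not purely hypothetical.

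**Conclusion.** The concern holds in a limited form. DFS, OS and local recurrence have no date other than one counted from a post-randomisation event, and the text does not settle what happens to patients who fail before that event or never reach it. For patients treated as scheduled, the effect is about a point of DFS and nearly the same in both arms. For the others, each patient is worth up to 2.4 points in one arm, in a comparison that rests on about 16 to 27 events. Their number is not given, so neither the size nor the direction of any bias can be stated. All DFS rates, failure counts and power figures here are assumptions. The structural point depends on none of them. It should be fixed.

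**What to change.** In 3.7, 3.8 and 3.13, count DFS and OS from randomisation in all randomised patients, with one common landmark: 3 years after randomisation, or about 173 weeks if the planned postoperative follow-up is to be kept. Code death or progression before surgery as not disease-free, state how a living unoperated patient is coded, and record unoperated patients on the same calendar. Say which origin local recurrence uses. State the time of randomisation in 3.10. Complications, hospital stay, readmission and resection margin stay postoperative.

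The removal of experimental mrTRG 5 patients in 3.4 must be reconciled with analysing everyone randomised. This concerns their data, not their treatment.

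The cost is a protocol amendment with text edits in those five sections, and a recheck of the hazard ratio of 0.23 and the 90% power, since that ratio may not carry over to the redefined endpoint. The 3-year landmark gives up about 17 weeks of postoperative follow-up; the 173-week landmark avoids that loss at the price of a later readout.

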3.8 Secondary endpoints

Secondary endpoints of the present study are:

Complete Pathological Response. Occurrence of Complete Pathological Response. If such an episode occurs, then it will be defined as=1 'YES' If such an episode does not occur, then it will be defined as=0 'NO'. [Time Frame: 1 month postoperatively]

Postoperative Complications. Occurrence of postoperative complications based on the Clavien Dindo Classification [20]. If such an episode occurs, then it will be defined as=1 'YES' If such an episode does not occur, then it will be defined as=0 'NO'. [Time Frame: 1 month postoperatively]

Length of Hospital Stay. Postoperative time that the patient can be safely discharged. Measurement unit: days. The patient will be discharged, when it is ensured that is medically safe

to be released. In particular, as the exit time of the patient, will be regarded the time that the patient will fulfil the Clinical Discharge Criteria. [Time Frame: Maximum time frame 39 days postoperatively]

Readmission. Occurrence of postoperative readmission. If such an episode occurs, then it will be defined as=1 'YES' If such an episode does not occur, then it will be defined as=0 'NO'. [Time Frame: 1 month postoperatively]

Negative Resection Margin. Occurrence of Negative Resection Margin. If such an episode occurs, then it will be defined as=1 'YES' If such an episode does not occur, then it will be defined as=0 'NO'. [Time Frame: 1 month postoperatively]

Overall Survival. Occurrence of Overall Survival. If such an episode occurs, then it will be defined as=1 'YES' If such an episode does not occur, then it will be defined as=0 'NO'. [Time Frame: 3 years postoperatively]

Chemotherapy Toxicity. Occurrence of Chemotherapy Toxicity. If such an episode occurs, then it will be defined as=1 'YES' If such an episode does not occur, then it will be defined as=0 'NO'. [Time Frame: 3 years postoperatively]

Local Recurrence. Occurrence of Local Recurrence. If such an episode occurs, then it will be defined as=1 'YES' If such an episode does not occur, then it will be defined as=0 'NO'. [Time Frame: 3 years postoperatively]

Treatment Compliance. Occurrence of Treatment Compliance. If such an episode occurs, then it will be defined as=1 'YES' If such an episode does not occur, then it will be defined as=0 'NO'. [Time Frame: 3 years postoperatively]

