severe toxicity from cytotoxic agents [14]. At the same time, according to the results of one of the largest prospective randomized trials, the addition of neoadjuvant chemotherapy into the treatment algorithm did not offer any advantage in the pathological response, 5-year overall and disease-free survival rates [15]. Finally, there is considerable heterogeneity in the current literature, most likely reflecting the different schemes used in different trials regarding the radiotherapy regimen, the chemotherapy regimen as well as the sequence of each one in each protocol [16].

We believe it is difficult to interpret any differences in results when multiple parameters have been changed in a comparative trial [17]. For this reason, when testing our current standard neoadjuvant protocol to the new trend of total neoadjuvant therapy we decided to keep the same scheme and timing for the experimental group also, and the only parameter which is different is the use of the classic chemotherapy scheme during the waiting period following chemoradiation and before surgery [18].

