3.9 Calculation of the sample size

The sample size calculation was based on the primary endpoint. According to the literature, the disease-free survival Hazard Ratio between standard practice and combined neoadjuvant therapy is 0.23 [21]. Therefore, for a prospective randomized study with alpha: 5%, power: 90% and dropout

rate: 15%, the estimated number of patients in each group is 42. A total of 84 patients will be required.

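### Postoperative complications rest on a severity-graded scale but are coded only any/none, so a shift from mild to severe at a constant overall rate would not show in the endpoint

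*Protocol*

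**What the plan says.** Protocol section 3.8 lists postoperative complications as a secondary endpoint: "Occurrence of postoperative complications based on the Clavien Dindo Classification". The coding follows at once: "If such an episode occurs, then it will be defined as=1 'YES' If such an episode does not occur, then it will be defined as=0" (that is, 'NO'). The window is "Time Frame: 1 month postoperatively". The section gives no grade cut-off, does not ask for a worst grade per patient and plans no tabulation by grade. No other section of the protocol brings severity back in.

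The toxicity endpoint has the same form: "Chemotherapy Toxicity. Occurrence of Chemotherapy Toxicity", coded yes/no over three years. No grading scale is named for it. Section 1.1, by contrast, gives the raised risk of severe toxicity as a specific reason for doubting neoadjuvant chemotherapy.

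On size, section 3.9 states "the estimated number of patients in each group is 42. A total of 84 patients will be required". That figure is derived for disease-free survival and includes 15% dropout.

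**The concern.** Clavien-Dindo ranks complications by severity. A yes/no variable with no threshold discards that ranking: on its natural reading, a grade I event and a death both score 1. If consolidation chemotherapy made complications worse without making them more frequent, the endpoint as defined would have the same expected value in both arms. The trial could then report no difference in complications while severe ones had risen.

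The point concerns the stated coding rule, not a detail left for later. The protocol fixes the variable, its two values and its time window.

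For toxicity there is a further problem. Section 3.4 plans oxaliplatin-based chemotherapy (or its alternative) in both arms, so some toxicity may be recorded for nearly everyone, and a yes/no variable would separate the arms poorly. That is an expectation; the protocol gives no toxicity rate.

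**Working it through.** The protocol states no complication rate and no power for this endpoint, so there is no figure to reproduce. All rates below are assumptions.

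**Inputs.**
- From section 3.9: 42 per arm and 15% dropout, so 42 × 0.85 = 35.7, about 36 evaluable per arm.
- From section 3.9: alpha 5%. Sidedness is not stated; two-sided is assumed here.
- Assumed control grades 0/I/II/III/IV/V: 50/15/20/10/3/2%. Any grade = 15 + 20 + 10 + 3 + 2 = 50%. Grade III or higher = 10 + 3 + 2 = 15%.
- Assumed experimental arm: any grade still 50%, grade III or higher doubled to 30%. Grades I–II fall from 35% to 20%, with proportions kept within each block.

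**Step 1: expected difference.**
- Any/none: 50% − 50% = 0 points, at any sample size.
- Grade III or higher: 30% − 15% = 15 points.

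**Step 2: power for the doubling, simulated with 36 per arm.** Pooled z-test for the two binary summaries, Mann-Whitney for the ordinal grade.

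| Summary | Power |
|---|---|
| Any/none | about 4% |
| Ordinal grade | about 8% |
| Grade III or higher | about 32% |

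The any/none figure is only the false-positive rate of the test. The ordinal test gains little because half of each arm is tied at grade 0 and the whole shift lies within the other half.

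**Step 3: check of the 32% by formula.** Power ≈ Φ[(Δ − 1.96·SE₀)/SE₁].
- Pooled rate = (0.15 + 0.30)/2 = 0.225.
- SE₀ = √(2 × 0.225 × 0.775/36) = 0.0984.
- SE₁ = √((0.15 × 0.85 + 0.30 × 0.70)/36) = 0.0968.
- (0.15 − 1.96 × 0.0984)/0.0968 = −0.44, and Φ(−0.44) ≈ 0.33, in agreement with the simulation.

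**Step 4: what an estimate would look like.** If 15% and 30% were observed, the 95% interval is 0.15 ± 1.96 × 0.0968, about −4 to +34 points. The shift is visible but not confirmed.

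**Step 5: other assumed rates for a doubling of grade III or higher, any-grade rate constant.**

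| Grade III or higher | Power, 36 per arm | Power, 42 per arm | Per arm for 80% power |
|---|---|---|---|
| 5% v 10% | 12% | 14% | 435 |
| 10% v 20% | 22% | 25% | 199 |
| 15% v 30% | 33% | 38% | 121 |

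**Step 6: patterns in which any/none does respond.**
- If the extra severe cases are new complications, a 40% any-grade rate rises to 45%, 50% or 55%. Power on any/none with 36 per arm is then 6%, 13% or 24%.
- If all grades shift together (proportional odds of 2.5, same control grades), power is about 47% on any/none, 57% on the ordinal grade and 35% on grade III or higher. Here any/none does better than the severe-only summary.

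**The case against.** The strongest reply is that no single summary is best. Under a proportional shift any/none beats grade III or higher, and no rate in the protocol says which pattern to expect. This stands. It is why the any-grade rate should stay and the grade be reported beside it, not in its place.

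A reader might infer that better coding would let this trial detect a doubling of severe complications. The figures do not support that: about 32% power on grade III or higher at 15% v 30%, and less at lower rates. Nor is an ordinal test the cure, with about 8% power in the same scenario.

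A reader might also infer that the grades are already collected. For complications this is only implied by naming the classification, since section 3.8 does not say that a worst grade per patient is recorded. For toxicity it is not even implied, because no scale is named.

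Three further replies carry partial weight.
- A statistical analysis plan, not shown, may add a table by grade. That would help, but the endpoint defined in the protocol would remain any/none.
- Length of stay, readmission and overall survival are separate endpoints in section 3.8, so prolonged stays and deaths would not vanish. They reflect complication severity only indirectly.
- Section 1.1 questions safety in general and names severe cytotoxic toxicity in particular; it does not name severe surgical complications. Its text on severity therefore supports the toxicity part of this point more directly than the surgical part.

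**Conclusion.** The point holds in a limited form. Section 3.8 names a graded scale and then fixes a yes/no variable with no threshold, so a mild-to-severe shift at a constant overall rate has an expected difference of zero. That follows from the definition and needs no assumed rate. It does require the extra severe cases to come from patients who would otherwise have had a milder complication; the protocol offers no evidence for or against this.

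The size depends wholly on assumed rates. The benefit of keeping the grade is chiefly descriptive: a difference such as 15% v 30% would appear, with a wide interval. The same coding weakness applies to chemotherapy toxicity, where no scale is named. Both are secondary endpoints, and neither the disease-free survival analysis nor the number of 84 is touched. The change is desirable, not essential.

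**What to change.** In section 3.8, for postoperative complications:
- record the worst Clavien-Dindo grade per patient within 1 month of surgery;
- report by arm the number and percentage with grade III or higher, with a confidence interval for the difference, and the full grade distribution;
- keep the existing any-grade rate beside them.

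An ordinal comparison is optional and should not be relied on to reveal a pure shift in severity.

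For chemotherapy toxicity, name a grading scale and report the worst grade per patient by arm beside the yes/no rate.

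The cost for complications is a sentence in section 3.8, one or two more summary lines, and recording of the grade if it is not already captured. Toxicity costs more, because a scale must be chosen and grades recorded. Clinical management, the primary analysis and the sample size do not change.

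### Chemotherapy toxicity and treatment compliance have a postoperative time frame with no stated start, while all consolidation chemotherapy is given before surgery

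*Protocol*

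**What the plan says.** Section 3.8 lists chemotherapy toxicity as a secondary endpoint coded yes or no: "Chemotherapy Toxicity. Occurrence of Chemotherapy Toxicity. If such an episode occurs, then it will be defined as=1 'YES". Compliance is built the same way: "Treatment Compliance. Occurrence of Treatment Compliance". Both carry the bracket "Time Frame: 3 years postoperatively", and neither has a start such as randomisation, first dose or start of chemoradiotherapy.

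Section 3.4 sets the order of treatment. Experimental patients who respond at re-staging are told that "they will receive consolidation chemotherapy for the whole waiting period between the end of CRT and surgery - 12 weeks", so consolidation ends before the operation. The objective in 2.1 agrees. For the control group 3.4 adds "Adjuvant chemotherapy will be, also, administered" after surgery, and the course is given as "Adjuvant Chemotherapy. 8 cycles of CAPOX" at three-week intervals, or 12 cycles of FOLFOX. Capecitabine with radiotherapy comes before surgery in both arms.

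Section 2.1 mentions adjuvant chemotherapy with the standard arm only, and 3.4 attaches it to that arm in the text on each group. Section 1.1 says instead that the arms differ in a single respect, the chemotherapy given in the waiting period. That could mean adjuvant treatment in both arms.

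**The concern.** The two strategies differ mainly in when systemic chemotherapy is given, and surgery is the dividing line. A window that opens at surgery falls on that line, so it would see one arm's chemotherapy and miss the other's.

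These two endpoints bear on questions that the protocol itself raises. Section 1.1 offers poor postoperative compliance as a possible reason why better local control did not bring better long-term survival, and it lists severe toxicity among the objections to giving chemotherapy before surgery. If toxicity during consolidation were not counted, the experimental arm would look safer than it is. If compliance with consolidation were not counted, the expected advantage in completing treatment could not be assessed.

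**Working it through.** There is no stated figure to reproduce. The check sets the endpoint window against the treatment sequence, using CAPOX because 3.4 gives its cycle length.

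**Inputs (section 3.4):** consolidation period 12 weeks, all before surgery; CAPOX cycle 3 weeks; adjuvant course 8 cycles, all after surgery.

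**Step 1, amount of treatment.** Consolidation: 12 / 3 = up to 4 cycles. This is an inference, since 3.4 states no number of consolidation cycles. Adjuvant: 8 × 3 = 24 weeks, well inside 3 years.

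**Step 2, planned cycles that fall in each window.**

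| Reading of the window | Adjuvant given to | Control | Experimental |
|---|---|---|---|
| Opens at surgery | control only (2.1, 3.4) | 8 of 8 | 0 of up to 4 |
| Opens at surgery | both arms (one reading of 1.1) | 8 of 8 | 8 of up to 8 + 4 = 12, i.e. 67% |
| Covers all study treatment, ends at 3 years | control only | 8 of 8 | 4 of up to 4 |
| Covers all study treatment, ends at 3 years | both arms | 8 of 8 | 12 of up to 12 |

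In both rows with a window that opens at surgery, the uncounted cycles are the treatment under test. FOLFOX has no stated cycle length, so its weeks cannot be computed. The pattern is the same: its 12 adjuvant cycles follow surgery and any consolidation FOLFOX precedes it. Capecitabine with radiotherapy would be missed in both arms and does not cause the asymmetry.

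**Step 3, which reading does the text support?** Two brackets in 3.8 cannot be observation windows. Pathological response ("Complete Pathological Response. Occurrence of Complete Pathological Response") and resection margin are framed at 1 month although the specimen fixes them at surgery, and 3.13 has the specimen's pathology recorded at about the one-month reassessment. There the bracket is a recording time. For complications and readmission ("Readmission. Occurrence of postoperative readmission") the same kind of bracket goes with a period that does begin at surgery. Usage within 3.8 therefore does not settle the meaning for toxicity and compliance.

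**Step 4, does a window over all treatment capture everything?** Not necessarily. Under 3.4 all experimental patients start consolidation, and those with mrTRG 5 at week 6 go to surgery and are then excluded from the trial. By then they may have had up to 6 / 3 = 2 CAPOX cycles (again inferred). The table's last two rows describe the full plan of patients who stay in. The exposure of excluded patients can be lost under either reading. No such exclusion is stated for control patients with mrTRG 5.

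**The case against.** The strongest reply is that the protocol never says counting begins at surgery. The bracket serves elsewhere as a recording time or an upper limit. Complications and readmission are called postoperative in their own definitions, so it is not the bracket that sets their start, and toxicity and compliance carry no such word. A window from surgery would also leave the experimental arm with no chemotherapy to comply with if adjuvant treatment is for control only, which is unlikely to be intended. Observation periods, grading and denominators are, moreover, often left to a statistical analysis plan.

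Much of this stands. A reader might infer that the toxicity comparison is certainly biased; the documents support only a bias conditional on one reading. A reader might also infer from 3.13, which describes follow-up after discharge and names neither endpoint, that toxicity before surgery will not be recorded. That section covers the period after discharge, so its silence proves nothing about earlier data collection.

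Two things remain. The time frame is fixed in the protocol, not left open, and as worded it can be applied in the lopsided way. And collection has to begin before surgery, so a later analysis plan could not reliably recover events that were never recorded.

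**Conclusion.** The point holds as an ambiguity with a conditional bias, and it is minor. If the window opens at surgery, it counts all 8 control adjuvant CAPOX cycles and none of the up to 4 consolidation cycles. The toxicity comparison then favours the experimental arm, and consolidation compliance is not measured. If the bracket marks only the recording time or the end of observation, this window bias does not arise.

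It would go too far to say that the second reading removes every difficulty, because experimental patients excluded after starting consolidation could still be missed. The size of any bias in toxicity rates cannot be given, since the protocol states no expected rates. The cycle counts assume CAPOX and a 12-week consolidation period filled with three-week cycles.

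**What to change.** In section 3.8:

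- State for both endpoints that observation runs from randomisation (or first study treatment) to 3 years after surgery, in both arms.
- Count all randomised patients, including experimental patients with mrTRG 5 who started consolidation.
- Judge compliance against each arm's own planned chemotherapy, before and after surgery.
- Report grade 3 or higher toxicity alongside the yes/no, because the concern in 1.1 is severe toxicity and an ungraded outcome cannot isolate it.

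Sections 1.1, 2.1 and 3.4 must be reconciled on whether the experimental arm's plan includes adjuvant chemotherapy. Until then the compliance denominator in that arm is undefined.

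The cost is a short addition to two secondary endpoints, slightly more data entry for the toxicity grade, and keeping the excluded patients' records for these endpoints. Sample size, power, primary analysis and treatment do not change.
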